6.2.3. Analysis of immunogenicity

The analysis will be performed on the ATP cohort for immunogenicity. If the percentage of vaccinated subjects with serological results excluded from the ATP cohort for analysis of immunogenicity is more than 10%, a second analysis will be performed on the TVC.

Humoral immune response

Within group evaluation

For each group, at each time point during which blood samples are collected for humoral immune response and for each assay:

- Seropositivity rate and their exact 95% CI will be tabulated.
- GMCs and their 95% CI will be calculated.

For each group, at each time point during which blood samples are collected for humoral immune response:

- Antibody concentrations distribution will be investigated using Reverse Cumulative Curves.

Between groups evaluation

Comparative analyses will be exploratory with the aim to characterise the difference between the 2 groups in humoral immune response.

The difference in terms of GMCs will be evaluated at 1 month post-Dose 2 and at Day 450 by computing the 95% CIs of the GMC ratio between groups by using an ANCOVA model that consider heterogeneity of variances (via Proc Mixed) on the logarithm10 transformation of the concentrations. This model will include the country, the group, age category (40 - 59 years or 60 - 80 years), number of moderate and severe AECOPD in the year before vaccine Dose 1 (< 2 or \geq 2), GOLD grade (GOLD 2 or GOLD 3) and pre-Dose 1 concentration (as covariate) as fixed effects.

However, these differences should be interpreted with caution considering that there will be no adjustment for multiplicity of endpoints.

Cell-mediated immune response

The frequency of specific CD4 $^{+}$ / CD8 $^{+}$ T-cells will be summarised (mean, SD, minimum, Q1, median, Q3, and maximum) by group, at each time point during which blood samples are collected for CMI (descriptive statistics).

Each data will be obtained by subtracting the summary of the background value to each summary value. Values less than or equal to zero will be set to 1 for the purpose of geometric mean calculation and graphical representation.

Statistical Analysis Plan

Study alias & e-track number(s): NTHi-004 (200157)

6.2.4. Analysis of impact of the investigational vaccine on AECOPD incidence

The analysis will be performed on the ATP cohort for efficacy. If the percentage of vaccinated subjects excluded from the ATP cohort for efficacy is more than 10%, a second analysis based on the TVC will be performed to complement the first analysis.

The following incidence rates will be computed over a period starting 1 month post-Dose 2 and lasting for 1 year, with 95%CI:

- NTHi-associated moderate and severe AECOPD. (See definition in section 7.1.4)
- NTHi-associated all-severity AECOPD.
- All-cause moderate and severe AECOPD.
- All-cause, all-severity AECOPD.

Vaccine efficacy (VE) for AECOPD events will be defined as:

$$VE(AECOPD) = 1 - R_{vaccine} / R_{control}$$

with:

- $R_{vaccine}$ = average yearly incidence rate of AECOPD events per subject in the group 10-AS01E.
- $R_{control}$ = average yearly incidence rate of AECOPD events per subject in the Control group.

In case the 95% CI of the VE cannot be estimated, *e.g.* when no event is observed in the group 10-AS01E (leading to a VE of 100%), then an exact procedure will be used to estimate a VE and its 95% CI. This exact procedure will be based on the number of subjects with event instead of on the average number of event per subject in each group.

VE in the prevention of NTHi-associated moderate and severe AECOPD and its 95% CI will be calculated.

VE in the prevention of NTHi-associated all-severity AECOPD, of all-cause moderate and severe AECOPD and of all-cause, all-severity AECOPD and their 95% CI will also be calculated.

The 95%CI of the incidence rate will be computed using a model which accounts for repeated events. The Generalised linear model assuming the Negative Binomial distribution for the response variable with logarithm as link function, and the logarithm of time for follow-up as an offset variable will be used. In addition, the following covariates (as per randomization) will be taken into account:

Statistical Analysis Plan

Study alias & e-track number(s): NTHi-004 (200157)

- country,
- number of moderate/severe exacerbations reported in the 12 months prior to enrolment,
- COPD status at enrolment (derived by GSK from the Visit 1 spirometry results)
- Age (below or equal to median/above median)

If the model does not converge, the Poisson distribution will be used instead of the Negative Binomial one.

The frequency of all these AECOPDs will be presented. The estimated incidence rate with 95%CI of AECOPDs in which Hi (resp. Mcat, Sp) is present in culture and was not present in the previous visit estimated by a Generalised linear model assuming the Negative Binomial distribution will be estimated.

Time to first AECOPD event by baseline status - Cox regression model

The Cox's regression model including the risk factors:

- country,
- number of moderate/severe exacerbations reported in the 12 months prior to enrolment,
- COPD status at enrolment (derived by GSK from the Visit 1 spirometry results)
- Age (below or equal to median/above median)

as covariates (as per randomization) will be performed to model the time until the first occurrence of AECOPD episodes. Additional stratification/risk factor may be defined during the analyses like sex factor as exploratory analysis.

6.2.5. AECOPD visits and daily questionnaires

The time until first AECOPD as of 1 month post-Dose 2 will be computed with exact 95% CI by group. Subjects who exacerbate before 1 month post-Dose 2 will not be taken into account in this analysis.

The number of morning e-dairy (PHT) alerts (resp. evening e-diary alerts (EXACT-PRO)) with and without corresponding site visits will be tabulated. The reason for inconsistency between morning e-diaries and site visits will also be presented.

The number of exacerbation site visits with confirmed AECOPD with and without morning e-diary alerts (resp. evening e-diary alerts (EXACT-PRO)) will be tabulated along with the reason for no e-diary alert.

Concordance/discordance of exacerbations periods as defined clinically or via the morning diary cards or the evening diary cards will be tabulated and presented graphically.

Statistical Analysis Plan

GlaxoSmithKline

Study alias & e-track number(s): NTHi-004 (200157)

The percentage of spontaneous exacerbation visits will be tabulated as well as the percentage of monthly visits with recovered/stable status.

6.2.6. Analysis of HRQOL, lung capacity and exercise capacity

The analysis will be performed on the TVC. If the percentage of vaccinated subjects excluded from the ATP cohort for efficacy is at least 10%, a second analysis will be performed on the ATP cohort for efficacy to complement the first analysis.

Descriptive statistics (median, mean, range, standard deviation, first and third quartiles) on the **EXACT-PRO, CAT, SGRQ-C** and **mMRC** scores, on **FEV₁% of predicted normal value** and on the **6MWT** scores will be tabulated by specified visit.

Descriptive summaries **rescue medication and healthcare use for AECOPD** will be provided.

6.2.7. Analysis of selected biomarkers

The analysis will be performed on the ATP cohort for efficacy. If the percentage of vaccinated subjects excluded from the ATP cohort for efficacy is at least 10%, a second analysis will be performed on the TVC to complement the first analysis.

For each type of timepoint (Pre, Exacerbation visit, Day 450) during which blood samples are collected for analysis of biomarkers, descriptive statistics (median, mean, range, standard deviation, first and third quartiles) will be tabulated for each selected biomarker.

6.2.8. Analysis of sputum

6.2.8.1. Sputum sample collection and quality

The proportion of subjects (at each stable and exacerbation visit) who provided a sputum sample will be computed; overall and by the sample method (spontaneous or induced).

The proportion of subjects with induced sputum will be tabulated by COPD status at enrolment and by severity of the AECOPD.

The distribution of the time (in days) between the start of exacerbation and the day of the sputum sample collection will be presented.

Statistical Analysis Plan

Study alias & e-track number(s): NTHi-004 (200157)

6.2.8.2. Sputum bacterial/viral results from culture or from PCR

The distribution of the proportion of sputum samples positive given the number of days between start of exacerbation and sample collection will be presented.

The proportion of sputum samples obtained at each - stable and exacerbation - visit and positive for specific bacterial/viral pathogens (overall and by bacterial culture, bacterial PCR, or viral species) will be computed. The average infection rate by type of visit will also be calculated.

The bacterial presence in culture versus the bacterial presence in PCR detected in sputum will be tabulated.

The viral infections versus the bacterial presence in PCR detected in sputum will be tabulated.

The incidence of exacerbations and of exacerbations containing Hi, Mcat, Sp, and all bacterial and/or virus that are planned to be tested by the laboratory will be presented.

For specific bacterial pathogens, the quantitative assessment of PCR results will be provided overall, for sputum samples positive in culture, or negative in culture of the specific pathogen.

6.2.8.3. Impact of previous antibiotic administration on sputum bacterial results

The impact of antibiotic administration before sputum collection on the bactericidal culture or PCR results will be evaluated, for stable (scheduled) visits, exacerbation visits, or any visit.

6.2.8.4. Impact of induction of sample on sputum bacterial results

The impact of sputum induction on the bactericidal culture or PCR results will be evaluated, for stable (scheduled) visits, exacerbation visits, or any visit.

6.2.8.5. Impact of previous occurrence of Hi bacterial pathogen in sputum on AECOPDs

The impact of the occurrence or presence of respiratory pathogenic bacteria detected in sputum at the exacerbation visit given the presence of the bacteria at previous visits on the number of exacerbations will also be studied. In order to do this, 2 types of AECOPDs will be distinguished:

- AECOPDs in which Hi is present and was not present any previous visit
- AECOPDs in which Hi is present and was not present in the previous stable visit;

Statistical Analysis Plan

Study alias & e-track number(s): NTHi-004 (200157)

7. STATISTICAL CALCULATIONS

7.1. Derived and transformed data

The study groups will be defined by treatment actually administered at Dose 1.

7.1.1. Demography

- For a given subject and a given demographic variable, missing measurement will not be replaced.
- Age: Age at the reference activity, computed as the number of units between the date of birth and the reference activity In case of partial dates of any of these 2 dates:
 - 15th of month, If only the day is missing
 - 30th of June, if day and months are missing

7.1.2. Safety

- For solicited symptoms, the analysis will exclude subjects with missing or un-evaluable measurements (*i.e.* total analysis of solicited symptoms will include all vaccinated subjects with documented solicited symptom sheets).
- For the unsolicited symptoms and concomitant medications/ products/ vaccinations, subjects who miss reporting symptoms/concomitant medications/ products/ vaccinations will be treated as subjects without unsolicited symptoms or concomitant medications/ products/ vaccinations, respectively.
- Note that for all tables described in this section, the way the percentage of subjects will be derived will depend on the event analysed (see table below for details). As a result, the N value will differ from one table to another.

Event	N used for deriving % per subject
Concomitant vaccination	All subjects with study vaccine administered
Solicited general symptom	All subjects with at least one solicited general symptom documented as either present or absent (i.e. symptom screen completed)
Solicited local symptom	All subjects with at least one solicited local symptom documented as either present or absent (i.e. symptom screen completed)
Unsolicited symptom	All subjects with study vaccine administered
Concomitant medication	All subjects with study vaccine administered

Study alias & e-track number(s): NTHi-004 (200157)

7.1.3. Immunogenicity

- For a given subject and the analysis of a given immunogenicity measurement, missing or un-evaluatable measurements will not be replaced.
- A seronegative subject is defined as a subject whose antibody concentration is below the assay cut-off value.
- A seropositive subject is defined as a subject whose antibody concentration is greater than or equal to the assay cut-off value.
- Antibody concentrations below the assay cut-off will be given an arbitrary value of half the assay cut-off for the purpose of geometric mean concentration (GMC) calculation.
- Calculation of the GMCs will be performed by taking the anti-logarithm in base 10 (anti-log10) of the mean of the log10 concentration transformations.
- The assay cut-off is the value under which there is no quantifiable result available. For an assay with a specific 'cut_off' , numerical immuno result is derived from a character field (rawres):
 - If rawres is 'NEG' or '-' or '(-)', numeric result= cutt_off/2,
 - if rawres is 'POS' or '+' or '(+)', numeric result = cut_off,
 - if rawres is '< value' and value<=cut_off, numeric result =cut_off/2,
 - if rawres is '< value' and value>cut_off, numeric result =value,
 - if rawres is '> value' and value<cut_off, numeric result =cut_off/2,
 - if rawres is '> value' and value>=cut_off, numeric result =value,
 - if rawres is '<= value' or '>= value' and value<cut_off, numeric result =cut_off/2,
 - if rawres is '<= value' or '>= value' and value>=cut_off, numeric result =value,
 - if rawres is a value < cut_off, numeric result = cut_off/2,
 - if rawres is a value >= cut_off, numeric result = rawres,
 - else numeric result is left blank.
- All CI computed will be two-sided 95% CI.

Impact of the investigational vaccine on AECOPD

- For a given subject and the analysis of a given laboratory assay, missing or un-evaluatable measurements will not be replaced.
- Subjects who did not have any sputum collected during at least 1 AECOPD (if at least 1 AECOPD occurred) will not be taken into account for the NTHI-associated AECOPD analyses.
- For summaries of the number of AECOPD occurring during the 1 year follow-up period starting 1 month post-Dose 2, an exacerbation rate will be calculated for each subject. The number of exacerbations during the 1-year follow-up period will be

Statistical Analysis Plan

Study alias & e-track number(s): NTHi-004 (200157)

imputed for subjects withdrawing from the study to provide an estimate of the number of exacerbations over the follow-up period. This calculation will only be performed for purposes of reporting summary statistics for the rate of exacerbations during the 1 year follow-up period since the modelling of exacerbations takes into account the number of exacerbations and the time of follow-up for each subject. The calculation of exacerbation rate will be based on follow-up period intervals to avoid obtaining high imputed rates if a subject withdrew very early in the follow-up period after experiencing an exacerbation. Since treatment courses for moderate/severe exacerbations are $\leq 2 - 4$ weeks when appropriate, calculated numbers of exacerbations for subjects withdrawing from the study will be based on 4-week intervals of the follow-up period. For subjects followed for less than 1 year, the number of exacerbations during the 1-year follow-up period will be calculated by multiplying the number of exacerbations experienced by the subject by 13 and dividing by the number of 4-week periods the subject was followed up:

Number of exacerbations per year = Number of exacerbations * 13 /Number of 4-week treatment period intervals

7.1.4. NTHi associated AECOPD

An NTHI associated to AECOPD is not yet well defined at the time of the SAP is written. Here is the first approach:

- An AECOPD for which NTHi was observed: Hi confirmed first by culture and then by PCR.

7.1.5. HRQOL

The CAT index will be derived as the sum of the ratings recorded for each of the eight individual items. Each of these items has 6 possible scores (0, 1, 2, 3, 4 or 5), leading to a range of 0 to 40 for CAT score.

7.1.6. EXACT-PRO derived AECOPD definitions and calculation rules

Start of an EXACT-PRO signal for exacerbation (as in EXACT-PRO user Manual and in Makay, et al., 2014):

1. *An EXACT-PRO exacerbation is defined as a 12 point increase above baseline for 2 consecutive days, or a nine point increase for 3 consecutive days.*
2. *The baseline score corresponds to the average EXACT score during a baseline period defined as days 14 to 8 preceding exacerbation onset*
3. *Exacerbation onset will be taken as the first day in which at least two symptoms (at least 1 major) are present and have not been discounted (see above).*

Statistical Analysis Plan

Study alias & e-track number(s): NTHi-004 (200157)

4. Only symptom data collected during the study period will be used to define the start of an exacerbation.

End/recovering of an EXACT-PRO signal of an exacerbation:

1. The end/recovering of an EXACT-PRO signal of an exacerbation corresponds to the day at the EXACT-PRO score return to its baseline value.
2. The length of a signal of an exacerbation will be at least of 2 days. So rule 1 will only apply from the third day onwards.

Missing data:

Days with missing data will not be ignored when defining start of a signal: e.g., if a patient has two qualifying symptoms followed by a missing day, if the next day with data has two qualifying symptoms this will not be defined as an exacerbation.

7.1.7. “e-diary derived AECOPD” definitions and calculation rules

The definition of an AECOPD case definition from section 5.3.1.2 of the Protocol ***is what we will call here an “e-diary derived (AECOPD) signal”***. In this paragraph, only the derivation of occurrence and length of ***e-diary*** signals is described. Derivation of occurrence and length of AECOPDs is described in Section 7.1.11.

Start of an e-diary signal for exacerbation:

1. An exacerbation is defined as a worsening of at least 2 symptoms for ≥ 2 consecutive days where at least one of the symptoms is major.
2. The same two symptoms do not have to be present on both days as long as at least one major symptom is present on both days.
3. Any symptom that has occurred consecutively for 5 days or more prior to a potential exacerbation should be discounted from the symptoms that define an exacerbation.
4. Exacerbation onset will be taken as the first day in which at least two symptoms (at least 1 major) are present and have not been discounted (see above).
5. Only symptom data collected during the study period will be used to define the start of an exacerbation.

Statistical Analysis Plan

Study alias & e-track number(s): NTHi-004 (200157)

7.1.8. End/Duration of an *e-diary* signal of an exacerbation:

1. The end/recovering of an *e-diary* signal of an exacerbation corresponds to the day at which the 3-day moving average of the daily symptom count score (average between the day the day before and the day after) to return to baseline symptom count score (the mean daily symptom count score over days 14 to 8 preceding exacerbation onset). For a specific day, the daily symptom count score is defined as the sum of the symptom scores experienced in this day (a major symptom accounts for 2 points, a minor symptom accounts for 1 point, as in Trappenburg *et al.*, 2011, but contrary to Seemungal *et al.* 2000 and Mackay *et al.* 2014, in which all symptoms accounted to 1). Note that the symptoms that have occurred consecutively for 5 days or more prior to a potential exacerbation and that are discarded for these exacerbations are not discarded from the symptoms counts.
2. The length of an *e-diary* signal of an exacerbation will be at least of 2 days. So rule 1 will only apply from the third day onwards.
3. The baseline symptom count score is calculated as the average count score of the observed days in the period used to calculate the baseline symptom count score. For example, if an exacerbation occurs from day 10 onwards, the baseline period will be the average between day1 and day2 (day10 - 8 days= day2, day10 - 9 days = day1, Day1 being the first study day). For exacerbations before day 9 but after day 2, the baseline symptom score will be considered to be day1
4. If the first *e-diary* signal of an exacerbation is occurring before day 3: duration will be counted until the day in which there is at most 2 majors or 1 major and one minor symptom.
5. Recovery time is calculated as the number of days from exacerbation *e-diary* signal onset (included) to exacerbation *e-diary* signal end (not included).

7.1.9. Time between 2 *e-diary* signals for exacerbations/evaluation of baseline symptom score:

The minimum duration between 2 *e-diary* signals with distinct baseline value is 15 days, which is the minimal period for which a new full exacerbation-free baseline can be calculated for the next *e-diary* episode.

If a new worsening of symptoms occurs between 6 and 14 days of a previous exacerbation, the baseline period used will be the same baseline as the one of the original exacerbation. Therefore, it will last until the daily symptom count score has gone below the baseline symptom score of the previous event.

Statistical Analysis Plan

Study alias & e-track number(s): NTHi-004 (200157)

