6.1.4. AECOPD visits and daily questionnaires

The time until first AECOPD as of 1 month post-Dose 2 will be computed with exact 95% CI by group. Subjects who exacerbate before 1 month post-Dose 2 will not be taken into account in this analysis.

The number of morning e-dairy (PHT) alerts (resp. evening e-diary alerts (EXACT-PRO)) with and without corresponding site visits will be tabulated. The reason for inconsistency between morning e-diaries and site visits will also be presented.

The number of exacerbation site visits with confirmed AECOPD with and without morning e-diary alerts (resp. evening e-diary alerts (EXACT-PRO)) will be tabulated along with the reason for no e-diary alert.

Concordance/discordance of exacerbations periods as defined clinically or via the morning diary cards or the evening diary cards will be tabulated and presented graphically.

The percentage of spontaneous exacerbation visits will be tabulated as well as the percentage of monthly visits with recovered/stable status.

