7.1.6. EXACT-PRO derived AECOPD definitions and calculation rules

Start of an EXACT-PRO signal for exacerbation (as in EXACT-PRO user Manual and in Makay, et al., 2014):

1. *An EXACT-PRO exacerbation is defined as a 12 point increase above baseline for 2 consecutive days, or a nine point increase for 3 consecutive days.*
2. *The baseline score corresponds to the average EXACT score during a baseline period defined as days 14 to 8 preceding exacerbation onset*
3. *Exacerbation onset will be taken as the first day in which at least two symptoms (at least 1 major) are present and have not been discounted (see above).*
4. *Only symptom data collected during the study period will be used to define the start of an exacerbation.*

End/recovering of an EXACT-PRO signal of an exacerbation:

1. *The end/recovering of an EXACT-PRO signal of an exacerbation corresponds to the day at the EXACT-PRO score return to its baseline value.*
2. *The length of a signal of an exacerbation will be at least of 2 days. So rule 1 will only apply from the third day onwards.*

Missing data:

Days with missing data will not be ignored when defining start of a signal: e.g., if a patient has two qualifying symptoms followed by a missing day, if the next day with data has two qualifying symptoms this will not be defined as an exacerbation.

Statistical Analysis Plan

Study alias & e-track number(s): NTHi-004 (200157)

7.1.7. “e-diary derived AECOPD” definitions and calculation rules

The definition of an AECOPD case definition from section 5.3.1.2 of the Protocol is what we will call here an “e-diary derived (AECOPD) signal”. In this paragraph, only the derivation of occurrence and length of e-diary signals is described. Derivation of occurrence and length of AECOPDs is described in Section 7.1.11.

Start of an e-diary signal for exacerbation:

1. An exacerbation is defined as a worsening of at least 2 symptoms for ≥ 2 consecutive days where at least one of the symptoms is major.
2. The same two symptoms do not have to be present on both days as long as at least one major symptom is present on both days.
3. Any symptom that has occurred consecutively for 5 days or more prior to a potential exacerbation should be discounted from the symptoms that define an exacerbation.
4. Exacerbation onset will be taken as the first day in which at least two symptoms (at least 1 major) are present and have not been discounted (see above).

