5. Only symptom data collected during the study period will be used to define the start of an exacerbation.

7.1.8. End/Duration of an e-diary signal of an exacerbation:

1. The end/recovering of an e-diary signal of an exacerbation corresponds to the day at which the 3-day moving average of the daily symptom count score (average between the day the day before and the day after) to return to baseline symptom count score (the mean daily symptom count score over days 14 to 8 preceding exacerbation onset). For a specific day, the daily symptom count score is defined as the sum of the symptom scores experienced in this day (a major symptom accounts for 2 points, a minor symptom accounts for 1 point, as in Trappenburg *et al.*, 2011, but contrary to Seemungal *et al.* 2000 and Mackay *et al.* 2014, in which all symptoms accounted to 1). Note that the symptoms that have occurred consecutively for 5 days or more prior to a potential exacerbation and that are discarded for these exacerbations are not discarded from the symptoms counts.
2. The length of an e-diary signal of an exacerbation will be at least of 2 days. So rule 1 will only apply from the third day onwards.
3. The baseline symptom count score is calculated as the average count score of the observed days in the period used to calculate the baseline symptom count score. For example, if an exacerbation occurs from day 10 onwards, the

Statistical Analysis Plan

Study alias & e-track number(s): NTHi-004 (200157)

baseline period will be the average between day1 and day2 (day10 - 8 days= day2, day10 - 9 days = day1, Day1 being the first study day). For exacerbations before day 9 but after day 2, the baseline symptom score will be considered to be day1

4. If the first e-diary signal of an exacerbation is occurring before day 3: duration will be counted until the day in which there is at most 2 majors or 1 major and one minor symptom.
5. Recovery time is calculated as the number of days from exacerbation e-diary signal onset (included) to exacerbation e-diary signal end (not included).

7.1.9. Time between 2 e-diary signals for exacerbations/evaluation of baseline symptom score:

The minimum duration between 2 e-diary signals with distinct baseline value is 15 days, which is the minimal period for which a new full exacerbation-free baseline can be calculated for the next e-diary episode.

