If a new worsening of symptoms occurs between 6 and 14 days of a previous exacerbation, the baseline period used will be the same baseline as the one of the original exacerbation. Therefore, it will last until the daily symptom count score has gone below the baseline symptom score of the previous event.

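### SAP 7.1.6 gives no rule for an EXACT-PRO baseline window that overlaps an earlier episode, so a relapse starting less than 15 days after that episode can be missed or ended too early in the descriptive tables

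*SAP*

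**What the plan says.** SAP Amendment 1, section 7.1.6, defines the evening-diary signal: "An EXACT-PRO exacerbation is defined as a 12 point increase above baseline for 2 consecutive days, or a nine point increase for 3 consecutive days". Item 2 sets the reference level: "The baseline score corresponds to the average EXACT score during a baseline period defined as days 14 to 8 preceding exacerbation onset". The episode closes by reference to the same level: "The end/recovering of an EXACT-PRO signal of an exacerbation corresponds to the day at the EXACT-PRO score return to its baseline value". A rise after that day is therefore a new signal with its own baseline. The section has its own start, end and missing-data rules, says nothing about a window that overlaps an earlier episode, and does not refer to 7.1.9. The wording is unchanged from SAP version 1.

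The morning symptom diary is handled separately. Section 7.1.7 limits its scope: "In this paragraph, only the derivation of occurrence and length of e-diary signals is described". Section 7.1.9 then says "The minimum duration between 2 e-diary signals with distinct baseline value is 15 days", and explains that this is the time "which is the minimal period for which a new full exacerbation-free baseline can be calculated for the next e-diary episode" needs. For a new worsening at 6 to 14 days, "the baseline period used will be the same baseline as the one of the original exacerbation".

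EXACT-PRO episodes are used in SAP 6.1.4, which tabulates alerts with and without site visits, and confirmed AECOPD with and without alerts. It adds: "Concordance/discordance of exacerbations periods as defined clinically or via the morning diary cards or the evening diary cards will be tabulated". Section 7.1.11.1 takes AECOPD events from clinically confirmed unscheduled visits, whether or not there was a diary signal.

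**The concern.** A baseline should describe the stable state. When two episodes are close together, the seven days from 14 to 8 before the second onset can lie partly or wholly in the first. Their mean then carries the first episode's raised scores. This has two effects. The second rise may not clear the threshold, so no EXACT-PRO episode is recorded. If it does clear, the score has less far to fall before recovery is declared, so the episode is shortened.

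In the 6.1.4 tables, either effect would look like disagreement between EXACT-PRO and the clinic or the morning diary, although it comes from the baseline rule. The SAP recognises the problem of an uncontaminated baseline for the morning diary, in the same 14-to-8 window, but leaves it open for EXACT-PRO.

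**Working it through.** **Inputs from SAP 7.1.6 and 7.1.9.** The window is days 14 to 8 before onset, 7 days. The threshold is at least 12 points for 2 days or at least 9 points for 3 days. The clean-baseline separation is 15 days (stated for the morning diary).

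**Assumptions, because the documents give no figures.** Each episode is a flat rise above the stable level, without noise. The first lasts L days and rises E1 points. The relapse rises E2 points and lasts at least 3 days. Onset is the first day of the raised score. The main range is L = 3 to 21 and E1 = E2 = 12, 15 or 20.

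**Reproducing the SAP's 15 days.** Let day 0 be the last day of the first episode and o the relapse onset day. The window runs from o − 14 to o − 8. All its days fall after day 0 when o − 14 ≥ 1, so o ≥ 15. This matches 7.1.9. With at least one recovered day between episodes, the onset days at risk are 2 to 14, which is 13 days.

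**Step 1: overlap.** Let k be the number of window days lying in the first episode (days −L + 1 to 0).

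| Onset day | 2 | 4 | 6 | 8 | 10 | 12 | 14 | 15 |
|---|---|---|---|---|---|---|---|---|
| L = 3 | 0 | 0 | 1 | 3 | 3 | 3 | 1 | 0 |
| L = 5 | 0 | 1 | 3 | 5 | 5 | 3 | 1 | 0 |
| L = 7 | 1 | 3 | 5 | 7 | 5 | 3 | 1 | 0 |
| L = 10 | 4 | 6 | 7 | 7 | 5 | 3 | 1 | 0 |
| L = 14 or 21 | 7 | 7 | 7 | 7 | 5 | 3 | 1 | 0 |

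**Step 2: apparent rise.** Apparent rise = E2 − (k/7) × E1. For equal rises:

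- 12 points: k = 1 gives 10.3 (detected on the 3-day rule); k = 2 gives 8.6 (missed). Missed when k ≥ 2.
- 15 points: k = 2 gives 10.7; k = 3 gives 8.6. Missed when k ≥ 3.
- 20 points: k = 3 gives 11.4; k = 4 gives 8.6. Missed when k ≥ 4.

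With k = 7 the apparent rise is zero.

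**Step 3: onset days missed, out of 13.**

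| First episode | 12 points | 15 points | 20 points |
|---|---|---|---|
| 3 days | 7 | 5 | 0 |
| 5 days | 9 | 7 | 5 |
| 7 days | 11 | 9 | 7 |
| 10 days or more | 12 | 11 | 10 |

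At 25 points a relapse is missed when k ≥ 5 (25 − 25 × 5/7 = 7.1). That is onset days 3 to 10 after a 10-day episode (8 of 13) and days 6 to 10 after a 7-day episode (5 of 13). These are counts of onset days, not probabilities, because the distribution of relapse times is unknown.

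**Step 4: unequal rises.** First 12, relapse 20: k = 6 gives 9.7 (detected) and k = 7 gives 8.0 (missed). First 12, relapse 24: k = 7 gives 12.0 (detected). First 20, relapse 12: k = 2 already gives 6.3 (missed).

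**Step 5: early ending.** Take L = 10, rises of 20, onset day 12. Then k = 3 and the apparent rise is 11.4, so the relapse is detected. Its baseline is 20 × 3/7 = 8.6 points too high, so recovery is declared while the score is still 8.6 points above the stable level.

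**Step 6: after the fix.** With the earlier baseline carried forward the (k/7) × E1 term disappears. A relapse of 12 points or more is detected on all 13 onset days.

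**The case against.** **The cited manual may settle it.** Section 7.1.6 says its start rules follow the EXACT-PRO user manual, which may contain a reset rule. This stands as a limit: what can be said is that the SAP text states none.

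**Section 7.1.9 might be read across.** SAP 6.1.4 calls EXACT-PRO alerts evening e-diary alerts. But 7.1.7 ties e-diary signals to the symptom-based case definition, and the recovery rule in 7.1.9 is worded for the daily symptom count. The ambiguity is a reason to state the rule.

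**The morning diary is not a like-for-like comparator.** A reader might infer that 7.1.9 protects the morning diary from missing relapses while EXACT-PRO is left exposed. The documents do not support that. Morning onset is worsening of symptoms on two consecutive days and uses no baseline score, so 7.1.9 protects only the end and duration of an episode. Its carry-forward is also stated only for 6 to 14 days.

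**At short gaps there may be no second event.** The site may judge the first exacerbation to be ongoing, a category in SAP 7.1.11.2. There would then be no second confirmed AECOPD lacking an alert. This is fair for some early relapses.

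**The consequence is small.** This stands in full. The EXACT-PRO endpoint is the daily score, summarised descriptively. Episodes enter only the alert and concordance tables.

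**Conclusion.** The gap is real and is in the current SAP. Applied as written, the rule can miss a relapse starting less than 15 days after an earlier EXACT-PRO episode. For equal rises of 12 to 20 points it does so on most onset days after a first episode of about a week or longer: 7 to 11 of 13 after 7 days, 10 to 12 of 13 after 10 days or more. A relapse that is detected can be ended too early. These sizes rest on assumed flat rises, equal severity and episode lengths that the documents do not give.

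Three stronger readings are tempting and not supported. First, that every relapse within two weeks is missed: very short first episodes, onsets near day 13 or 14, and a much worse relapse can still be detected. Second, that AECOPD rates or vaccine efficacy are biased: these count clinically confirmed visits. Third, that the bias feeds into refining the AECOPD case definition: protocol 1.2.2.1 speaks of information from AECOPD-driven visits and calls, and does not mention EXACT-PRO signals or concordance. Nor do the documents show how many relapses are affected or in which patients.

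This is a worthwhile clarification of a descriptive analysis, not a threat to the trial's main results.

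**What to change.** Add one rule to SAP 7.1.6 item 2: *If any of days 14 to 8 before onset belongs to an earlier EXACT-PRO episode, the baseline of that earlier episode is used for both onset and recovery of the new episode.* Before finalising it, check the user manual; if the manual has its own reset rule, state that rule in the SAP.

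The trigger should be overlap of the window. Copying the 6-to-14-day wording of 7.1.9 would leave onsets on days 2 to 5 uncovered. The rule should also be the only one for overlap: excluding contaminated days and averaging the rest would conflict with carrying the earlier baseline forward.

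The cost is one sentence and minor programming, with no new data. The small downside is an older baseline for these relapses. For example, after a 10-day episode (days −9 to 0) the carried-forward window is days −23 to −17, so a relapse on day 8 is compared with scores from 25 to 31 days before it.
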